## 6. A Priori Statistical Methods

Statistical analysis of this study will be the responsibility of Eli Lilly and Company or its designee. The study PK scientist will be responsible for designing, conducting, and interpreting the PK analysis and delivering PK parameters. The interpretation of final study results will be the responsibility of the clinical research physician (CRP) and the study statistician.

Exploratory statistical analysis procedures not specified in the present document will be executed as deemed appropriate by the statistician and study team.

The following general terms will be used globally in the SAP:

- Unless otherwise specified, summary statistics stand for the number of patients with an observation (n), mean, standard deviation, median, minimum, and maximum for continuous variables; and population size (N), the number of events, the number of subjects with events (n) and the proportion of subjects with events ( $p=n/N$ ) for categorical variables.
- **Safety population** will consist of subjects who receive any amount of study drug. The safety population will be used for all analyses of dosing, exposure and safety.
- **DLT-evaluable population** will consist of: 1) subjects who receive at least 1 dose of the study drug and then experience DLT during Cycle 1; and 2) subjects who receive at least 85% of the prescribed dose in Cycle 1 and have an adverse event (AE) assessment in the first cycle. Dose-limiting toxicity-evaluation population will be used for evaluation of each dose level for dose-escalation.
- **Pharmacokinetic population** will include subjects who have sufficient PK data to derive at least one PK parameter.
- **Efficacy population** will include all patients who receive any quantity of study treatment at the dose recommended.

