### 6.5. Efficacy Analyses

#### 6.5.1. Efficacy Analysis Variables

Definition of efficacy analysis variables are listed below:

- **Objective response rate (ORR)** is defined as the proportion of treated patients achieving a best overall response of partial response (PR) or complete response (CR) per Response Evaluation Criteria in Solid Tumors Version 1.1(RECIST v.1.1). Patients who do not have any postbaseline tumor response assessments for any reason are considered nonresponders and are included in the denominator when calculating the response rate.
- **Disease control rate (DCR)** is defined as the proportion of treated patients achieving a best overall response of CR, PR, or stable disease (SD) per RECIST v.1.1. Patients who do not have any postbaseline tumor response assessments for any reason are considered non-responders and are included in the denominator when calculating the response rate.
- **Duration of response (DOR)** is defined from the date of first documented CR or PR (responder) to the date of objective progression or the date of death due to any cause, whichever is earlier. If a responder is not known to have died or have objective progression, then the patient will be censored at the date of last evaluable tumor assessment.
- **Progression-free survival (PFS)** is defined as the time from the date of randomization until the date of radiographic documentation of progression (as defined by RECIST v. 1.1) based on investigator assessment or the date of death due to any cause, whichever is earlier. The censoring is taken in the following order:
  - If a patient does not have a baseline disease assessment, then the PFS time will be censored at the randomization date, regardless of whether or not objective progressive disease (PD) or death has been observed for the patient.
  - If a patient is not known to have died or have investigator-assessed PD as of the data-inclusion cut-off date for the analysis, the PFS time will be censored at the date of last postbaseline adequate radiological tumor assessment, or at the date of randomization if the patient does not have any postbaseline adequate radiological assessment.

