- **Overall survival (OS)** is defined as time from the date of randomization to the date of death from any cause. For each patient who is not known to have died as of the data inclusion cut-off date for a particular analysis, OS will be censored for that analysis at the date of last contact prior to the data-inclusion cut-off date (contacts considered in the determination of last contact date include AE date, lesion assessment date, visit date, and last known alive date).

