### **6.5.2. *Description of Efficacy Analyses***

Best overall response is the best response recorded from the start of treatment until disease progression, in the order of CR, PR, and SD. Best overall response will be summarized for all patients evaluable for efficacy whose disease is assessable by RECIST 1.1.

If appropriate, the following analyses will be performed.

- Objective response rate will be estimated and reported for each dose level.
- Disease control rate will be summarized and provided for each dose level.

- Progression-free survival will be estimated using a Kaplan-Meier method (Kaplan and Meier 1958) by median and 95% confidence interval (CI). Additional exploratory analyses using proportional hazards models to control for other factors may be performed.
- Overall survival will be summarized using the Kaplan-Meier method.

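### PFS and OS start at a randomisation date that this trial does not have, and Kaplan-Meier OS is listed although scheduled follow-up stops 30 days after the last dose

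*SAP*

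**What the plan says.** **Time origin.** In SAP 6.5.1, OS "is defined as time from the date of randomization to the date of death from any cause" and PFS "is defined as the time from the date of randomization until the date of radiographic documentation of progression". Two PFS fallback rules use the same date. Without a baseline disease assessment, "then the PFS time will be censored at the randomization date". A patient with no death or progression is censored at the last adequate scan, "or at the date of randomization if the patient does not have any postbaseline adequate radiological assessment".

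**OS analysis.** SAP 6.5.2 states: "Overall survival will be summarized using the Kaplan-Meier method". This stands in a list of analyses to be done if appropriate, with no criterion for what is appropriate. Patients not known to have died are censored at last contact, and the contacts that count include "visit date, and last known alive date".

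**Population and other origins.** The efficacy population in SAP 6 "will include all patients who receive any quantity of study treatment at the dose recommended". For response, SAP 6.5.2 already runs from treatment: "Best overall response is the best response recorded from the start of treatment until disease progression". Protocol 12.7.2 also measures stable disease from the start of treatment.

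**Design and follow-up.**
- Protocol 5.1 and 5.3.1 describe an open-label study. Protocol 3.10 assigns the dose level at enrolment. Part B is a single group at the MTD or RP2D.
- The design schema and protocol 10.1 end therapy at progression. Protocol 10.1 follows patients off therapy until an off-study criterion is met.
- Protocol 10.2 sets off-study at 30 days after the last dose, or earlier for reasons such as joining another COG therapeutic study.
- The last column of the protocol 8.1 evaluation table is 30 days after the last dose.

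**The concern.** There are two separate faults.

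The first is that PFS, OS and two censoring rules refer to a date that will not be in the database. A programmer would have to choose enrolment or first dose, and the SAP does not say which.

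The second is that Kaplan-Meier requires censoring to be unrelated to the risk of death among those still at risk. Here progression stops therapy, and stopping therapy starts a clock of at most 30 days to the end of follow-up. Patients are therefore censored just as their risk of death has very probably risen, and the curve is carried by those who have not yet progressed. If few later deaths reach the database, reported survival would be too high. In a paediatric study with no control group, such a curve could be read as evidence of activity.

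**Working it through.** The documents give no expected survival, event count or precision for PFS or OS, so there is no figure to reproduce. The check has four steps.

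**1. Is there a randomisation date?** Part A is rolling-six escalation plus a pharmacokinetic expansion, and SAP 5.3 assigns dose by numbers enrolled, DLTs seen and data pending. Part B is one group at one dose. Randomised trials appear only in the adult background. So no such date exists. Protocol 3.9 puts projected first dose no more than 5 days after enrolment, which bounds the effect of the choice at about 5 days.

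**2. When does scheduled follow-up end?** Inputs from protocol 5.1 and the design schema: 42-day cycles; doses on Days 1, 15 and 29; at most 8 cycles; scans at the end of cycles 1 and 2, then every other cycle. For a scan at the end of cycle c:

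- scan day = 42c
- last dose = 42(c − 1) + 29 = 42c − 13
- off study = last dose + 30 = 42c + 17

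| Cycle | Scan day | Last dose | Off study |
|---|---|---|---|
| 1 | 42 | 29 | 59 |
| 2 | 84 | 71 | 101 |
| 4 | 168 | 155 | 185 |
| 6 | 252 | 239 | 269 |
| 8 | 336 | 323 | 353 |

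Progression found at a scheduled scan leads to off-study 17 days later. Progression found between scans gives 30 days minus the time since the last dose, so never more than 30. Without delays, nobody has scheduled follow-up beyond Day 353.

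**3. How large could the bias be?** This rests on assumed values. I took exponential times with median time to progression of 1.5 or 2.5 months, median survival after progression of 2, 4 or 6 months, and median survival before progression of 12 months, 24 months, or no such deaths. Each scenario has 200,000 simulated patients, doses every 14 days from Day 1 to Day 323, scans as above, and censoring at last dose + 30 days. Progression is detected at scans only, promptly, or half and half.

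Bias = Kaplan-Meier 6-month OS minus true 6-month OS, in percentage points, with no later deaths captured. Each range covers the six pairs of progression and post-progression medians:

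| Survival before progression | Scans only | Half prompt | All prompt |
|---|---|---|---|
| No deaths | 9.0 to 13.3 | 12.3 to 19.0 | 16.6 to 28.0 |
| Median 24 months | 6.5 to 11.3 | 8.3 to 16.1 | 11.4 to 23.6 |
| Median 12 months | 3.8 to 9.2 | 5.1 to 13.1 | 6.9 to 19.4 |

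Further settings:
- Also stopping for other reasons (median 12 months, with pre-progression median 24 months) changes these by at most 0.5.
- Later deaths captured for one year after off-study: 25% captured gives −0.7 to +15.8; 50% gives −4.0 to +8.7; 100% gives −7.3 to −0.2. The sign turns because patients who die are then followed to death, while survivors are still censored at 30 days.
- If the risk of death is unrelated to leaving therapy, the bias is within 0.3.

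**4. How does this compare with random error?** About 18 evaluable patients are planned at the recommended dose (12 in Part A plus 6 in Part B). With no late capture, 8% to 50% of patients have an observed death, which is 1.4 to 9.1 of 18. In simulated trials of 18 patients, the mean number at risk at 6 months is 1.2 to 7.5. Even without censoring, the 95% half-width at a survival of 0.5 is 1.96 × √(0.25/18) = 0.231. Because the efficacy population counts treated patients, one can inflate for the protocol's 20% inevaluable rate: 12/0.8 = 15 and 6/0.8 = 7.5, rounded up to 8, total 23. The half-width is then 1.96 × √(0.25/23) = 0.204.

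**The case against.** The strongest reply has four parts.

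- **The origin is a wording slip.** Any analyst would use enrolment or first dose, and the two nearly coincide. This is right about size. It does not make the definition usable as written, and the slip occurs in four rules.
- **OS is conditional and minor.** It is to be done only if appropriate, in support of a preliminary secondary aim that protocol 11.5 treats descriptively. This also stands. But the SAP gives no criterion, and the follow-up rules already show that the estimate is not supported.
- **Later deaths may be captured.** SAP 6.5.1 accepts a later date on which a patient is known to be alive, SAP 6.7.3 summarises deaths after 30 days, and protocol 13.1 requires related events and deaths beyond 30 days to be reported. Under protocol 10.1, patients removed in cycle 1 may be observed longer; allowing for that lowers the bias by at most about 1 point. The data forms are in a separate CRF packet (protocol 14.1) not seen here, so the degree of capture, and hence the sign of the bias, is not settled by the documents. None of these routes is scheduled survival follow-up, however, and the protocol 13.1 route covers only related events, so ascertainment may be selective.
- **Random error is as large as the bias.** With 18 to 23 patients it is about 20 to 23 points. That is true, and it weakens the case for keeping the curve.

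**Conclusion.** The concern holds. That no randomisation date exists and that no survival follow-up is scheduled beyond 30 days after the last dose both follow from the text and need no assumption.

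The direction of the OS bias is probable rather than certain. It is upward if few later deaths are captured, about zero if leaving therapy is unrelated to the risk of death, and slightly downward if later deaths are captured but survivors are not followed. The figures (4 to 28 points upward with no late capture, −4 to +9 with half captured, −7 to 0 with all captured) illustrate assumed medians and do not estimate this trial's error.

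MTD, RP2D and pharmacokinetic conclusions do not depend on any of this. It should be corrected because the rules are wrong as written and the remedy is cheap.

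**What to change.** 1. In SAP 6.5.1, replace the randomisation date with the date of first dose for PFS, for both PFS fallback censoring rules, and for OS if any OS definition is kept. First dose matches the treated efficacy population and the start-of-treatment origin already used for best response and stable disease.
2. In SAP 6.5.2, delete the Kaplan-Meier OS estimate. Protocol 11.6.7 names best response, duration of response and duration of stable disease, not OS, and protocol 12.7.2 reports those durations descriptively rather than as time-to-event analyses.
3. Report deaths on therapy and within 30 days of the last dose descriptively, in line with the death listing in protocol 11.6.7, and state that the window runs from the last dose.
4. Add a note to SAP 6.7.3 that no follow-up is scheduled for deaths later than 30 days, so that summary may be incomplete.

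The cost is SAP wording, with no new data or visits. One exploratory output is lost, which the scheduled follow-up does not support.

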### **6.5.2. *Description of Efficacy Analyses***

Best overall response is the best response recorded from the start of treatment until disease progression, in the order of CR, PR, and SD. Best overall response will be summarized for all patients evaluable for efficacy whose disease is assessable by RECIST 1.1.

If appropriate, the following analyses will be performed.

- Objective response rate will be estimated and reported for each dose level.
- Disease control rate will be summarized and provided for each dose level.

- Progression-free survival will be estimated using a Kaplan-Meier method (Kaplan and Meier 1958) by median and 95% confidence interval (CI). Additional exploratory analyses using proportional hazards models to control for other factors may be performed.
- Overall survival will be summarized using the Kaplan-Meier method.

## 6.6. Bioanalytical and Pharmacokinetic/Pharmacodynamic Methods

All PK/PD analysis and creation of table, figures, and listings will be the responsibility of Lilly Global PK/PD and Pharmacometrics group based on applicable Global PK/PD and Pharmacometrics Standard Operating Procedures and software approved by Global PK/PD and Pharmacometrics group's management.

## 6.7. Safety Analyses

All patients who receive at least 1 dose of study therapy will be summarized for safety and toxicity. Dose-limiting toxicity will be listed for Phase 1a only by ramucirumab dose schedules. Please refer to the protocol for the definition of DLT.

The descriptions and grading scales found in the revised National Cancer Institute (NCI) Common Terminology Criteria for Adverse Events (CTCAE) version 4.0 will be utilized for AE reporting. Unless otherwise specified, when summarized by Preferred Term (PT), AEs will be presented in decreasing frequency of PT across dose levels; when summarized by System Organ Class (SOC) and PT, AEs will be presented in decreasing frequency of PT within SOC across dose levels.

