5.0 TREATMENT PROGRAM

5.1 Overview of Treatment Plan

Treatment Schedule Table		
Day	Ramucirumab (i.v. over 60 minutes)	Disease Evaluation
1	X	
15	X	

THIS PROTOCOL IS FOR RESEARCH PURPOSES ONLY, SEE PAGE 1 FOR USAGE POLICY

29	X	
42		X

A cycle of therapy is considered to be 42 days. A cycle may be repeated for a total of 8 cycles, up to a total duration of therapy of approximately 12 months. This is an open-label study.

Effort should be made to begin protocol therapy on Monday through Thursday if possible to accommodate correlative sample shipments.

Drug doses should be adjusted based on actual weight measured within 7 days prior to the beginning of each cycle.

Update: With the release of Amendment #2A, the dose escalation portion of the study is complete. Given this, Part B will open to patients with relapsed or refractory CNS tumors.

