11.6 Statistical methods

11.6.1 **Analysis Sets**

Safety Analysis Set (SAS) will consist of subjects who receive any amount of study drug.

11.6.2 **Dose Evaluable Set (DES)** will consist of: 1) subjects who receive any amount of study drug and then experience DLT during Cycle 1; and 2) subjects who receive at least 85% of the prescribed dose in Cycle 1 and have an adverse event assessment in the first cycle. DES will be used for evaluation of each dose level for dose-escalation.

11.6.3 **Pharmacokinetic Analysis Set (PAS)** will include subjects who have sufficient PK data to derive at least one PK parameter.

11.6.4 **Efficacy Analyses:**

Preliminary efficacy analyses will also be performed by dose cohort for the Safety Analysis Set. Data cut-off for primary study analysis will occur when all enrolled subjects have completed 6 cycles of treatment or discontinued study drug administration. After the final analysis, additional analyses may be performed as appropriate.

11.6.5 **Pharmacokinetic Analyses**

Serum concentrations of Ramucirumab will be tabulated and summarized by dose level and time. Ramucirumab PK parameters will be derived from serum concentrations by non-compartmental analyses using actual times. Minimally, the following PK parameters will be calculated: C_{max} , t_{max} , and $AUC (t_{1/2}, CL, and Vd_{ss})$ will be calculated only if the data permit). Additional analysis utilizing the population pharmacokinetic approach may also be conducted if deemed appropriate.

11.6.6 **Immunogenicity Analyses**

Immunogenicity incidence will be tabulated, and correlation of immunogenicity to ramucirumab drug level, activity, and safety will be assessed as appropriate.

11.6.7 **Statistical Analyses**

Baseline demographics and baseline disease characteristics will be summarized for all enrolled patients who had at least one dose of study therapy.

Listing of patients including those treated at the MTD will be generated.

Treatment-emergent CTCAEs will be summarized by each dose level and for

THIS PROTOCOL IS FOR RESEARCH PURPOSES ONLY, SEE PAGE 1 FOR USAGE POLICY

overall population by each CTCAE grade separately.

Best overall response, duration of response, and duration of stable disease will also be summarized descriptively by each dose level.

Listing of deaths on study or 30 day post-discontinuation will be provided. Listing of SAEs will also be produced. Listing of AEs leading to treatment discontinuation will be provided.

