## 4. Study Objectives

### 4.1. Primary Objective

The primary objectives of the study are as follows:

- to estimate the maximum tolerated dose (MTD) and/or recommended Phase 2 dose (RP2D) of ramucirumab administered as an intravenous (IV) infusion over 60 minutes, every 2 weeks, to children with recurrent or refractory solid tumors
- to determine the tolerability of the MTD and/or RP2D of ramucirumab in children with recurrent or refractory central nervous system (CNS) tumors
- to define and describe the toxicities of ramucirumab administered on this schedule
- to characterize the pharmacokinetics (PK) and immunogenicity of ramucirumab in children with recurrent or refractory solid tumors including CNS tumors

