### 5.2. Determination of Sample Size

The primary objective for the dose-escalation phase and the dose-expansion cohort in Part A is to evaluate safety and tolerability in patients with non-CNS solid tumors for the purpose of determining a RP2D; the primary objective in Part B is to evaluate safety in patients with CNS tumors at dose selected as the RP2D in Part A. The sample size of each part of the study is selected to allow adequate assessment of safety at the recommended dose for ramucirumab.

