#### Part B:

Once the RP2D has been determined in Part A, Part B will open to enroll children with relapsed or refractory CNS tumors who will receive ramucirumab at the MTD or RP2D. Part B of the study will require up to 6 evaluable patients enrolled at the MTD/RP2D as determined in Part A. Allowing for 20% inevaluability, 8 patients may be enrolled.

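### The SAP's only DLT output is limited to an undefined Phase 1a, so read literally no DLT listing or n/N is planned for Part B, although CNS tolerability is a primary objective

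*SAP*

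**What the plan says.** - **DLT output.** SAP 6.7: "Dose-limiting toxicity will be listed for Phase 1a only by ramucirumab dose schedules". No other output in SAP 6.7 to 6.9 or Protocol 11.6 is a DLT listing, count or rate.
- **Use of the DLT population.** SAP 6: "Dose-limiting toxicity-evaluation population will be used for evaluation of each dose level for dose-escalation". Protocol 11.6.2 matches: "DES will be used for evaluation of each dose level for dose-escalation".
- **Default population.** SAP 6: "The safety population will be used for all analyses of dosing, exposure and safety".
- **Status of escalation.** Protocol 5.1: "With the release of Amendment #2A, the dose escalation portion of the study is complete". The same update says that Part B will open as a result.
- **Objective.** SAP 4.1 lists as primary "to determine the tolerability of the MTD and/or RP2D of ramucirumab in children with recurrent or refractory central nervous system (CNS) tumors". SAP 5.2 adds: "the primary objective in Part B is to evaluate safety in patients with CNS tumors at dose selected as the RP2D in Part A".
- **Size of Part B.** SAP 5.2: "Part B of the study will require up to 6 evaluable patients enrolled at the MTD/RP2D as determined in Part A", with 8 enrolled. Protocol 11.1 allows expansion to 12 evaluable (15 enrolled) if two DLTs of different classes occur.
- **Table grouping.** TEAE summaries are by dose level (SAP 6.7.2, Protocol 11.6.7) and exposure is by dose group (SAP 6.7.1). The AE overview is by *study arm* (SAP 6.7.2), which is not defined. SAP 5.1 describes Part B as a safety evaluation specific to CNS patients.

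**The concern.** The analysis plan should say how each primary objective will be reported. For tolerability in CNS tumors it names no DLT display, and the one DLT sentence it contains appears to leave those patients out. A programmer who follows that sentence would produce DLTs for Part A, or only for its escalation phase, and none for Part B.

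The ordinary AE tables do not supply DLT status. Under Protocol 5.5 a DLT depends on attribution, on duration exclusions for some Grade 3 events, on blood pressure relative to the 95th percentile, on a confirmed urine protein/creatinine ratio, on treatment delays, on platelet findings on two separate days, and on some Grade 2 events. None of this can be read from a table by preferred term and maximum grade.

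A second consequence concerns layout. Protocol 5.3.1 reports the RP2D as 12 mg/kg, which is also Part A dose level 2. A table split only by dose could merge CNS and non-CNS patients in one column.

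**Working it through.** **1. What Phase 1a could mean.** The term occurs once, in SAP 6.7. Three readings are possible.

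| Reading | Part A escalation | Part A PK expansion | Part B |
|---|---|---|---|
| Escalation phase only | listed | not listed | not listed |
| All of Part A | listed | listed | not listed |
| Leftover label, whole study meant | listed | listed | listed |

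Only the third reading covers Part B, and it gives the word *only* no function. The first also drops the PK expansion, whose DLTs Protocol 11.2.2 counts together with those at the MTD.

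**2. Whether another provision fills the gap.** The membership rule of the DLT-evaluable population would fit Part B patients: a DLT in Cycle 1, or at least 85% of the Cycle 1 dose with an AE assessment. Its stated use is dose-escalation, which was complete before Part B opened, so that use cannot reach Part B. What is missing is a stated use, not a definition.

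**3. The plan's own Part B numbers.** With 20% inevaluable:
- 6 / (1 − 0.20) = 7.5, rounded up to 8
- 12 / (1 − 0.20) = 15

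Both stated figures reproduce. Part B is therefore sized in evaluable patients.

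**4. What the missing display would show.** Exact (Clopper-Pearson) 95% intervals in evaluable patients, for illustrative DLT counts:

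| DLTs / evaluable | Rate | 95% CI |
|---|---|---|
| 0/6 | 0% | 0 to 45.9% |
| 1/6 | 16.7% | 0.4 to 64.1% |
| 2/6 | 33.3% | 4.3 to 77.7% |
| 4/12 | 33.3% | 9.9 to 65.1% |

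These are wide, as expected in a descriptive phase 1 cohort. The n/N is what readers would need.

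**5. Why the denominator should be named.** Two DLTs give 2/6 = 33.3% of evaluable patients, 2/7 = 28.6% if 7 are treated, and 2/8 = 25.0% if all 8 are treated. This illustrates that the denominator should be written down. It does not predict which one would be used.

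**6. Possible pooling at 12 mg/kg.** Protocol 5.3.1 plans 12 evaluable Part A patients at the RP2D; Part B plans 6. A merged column would hold 12 + 6 = 18, of whom 6/18 = 33.3% have CNS tumors. For illustration, an event in 2 of 6 CNS and 0 of 12 non-CNS patients would appear as 2/18 = 11.1%. Treated numbers may differ somewhat from these evaluable numbers.

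**The case against.** **The label may be a leftover.** Neither document mentions a Phase 1b, and the sentence refers to dose schedules although the study has one schedule with several dose levels. If the label is carried over, *only* may be too. This stands. A reader might infer a deliberate decision to exclude Part B; the documents do not show one. The wording still needs correction, because a programmer would follow it as written.

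**The denominator is already implied.** A reader might infer that a Part B DLT rate would default to all treated patients and so slip below the protocol's one-third threshold, for example 2/8 in place of 2/6. The documents do not support that. Protocol 11.2.1 replaces patients who are not evaluable for toxicity, Protocol 11.2.2 counts DLTs among evaluable patients, and SAP 5.2 sizes Part B in evaluable patients. The one-third rule defines the MTD and is applied during conduct, not to a final table.

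**Part B safety is not left unanalysed.** This also stands. SAP 6.7.2 and 6.7.3 list all AEs, and those leading to discontinuation or dose modification, which is where most DLTs would surface in 6 to 8 patients. The study chair records DLT evaluations and these are reviewed weekly (Protocol 14.4.2), so the decision to expand Part B does not rest on the SAP listing. No DLT flag or Part B n/N is specified, however.

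**CNS tolerability is not defined as a DLT rate.** True: Protocol 1.1.2 gives no measure, and Protocol 5.5 sets the DLT window for dose-escalation. But Protocol 11.1 ties expansion of Part B to DLTs, so they are the natural quantity to report.

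**Pooling is possible, not planned.** *Study arm* might be meant to separate the parts. It is undefined, and SAP 5.1 states the CNS-specific intention without a matching table.

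**Conclusion.** The point holds as a reporting gap that should be corrected before the final analysis. Read literally, the SAP plans no DLT listing or n/N for Part B, a cohort of up to 6 evaluable patients (12 if expanded) whose tolerability is a primary objective. The AE and exposure tables do not guarantee a separate view of these patients at 12 mg/kg.

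The conclusion rests on two things: Phase 1a is undefined, and no other SAP or Protocol 11.6 output covers Part B DLTs. It does not rest on any intent to exclude Part B, on a flaw in live safety monitoring, or on a likely wrong conclusion from the choice of denominator. The DLT counts above are illustrative; the documents give no Part B results.

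**What to change.** 1. Replace the DLT sentence in SAP 6.7 with: *DLTs will be listed and summarised (n/N) in the DLT-evaluable population, separately for Part A by dose level (escalation and PK expansion combined at the RP2D, per Protocol 11.2.2) and for Part B.*
2. In SAP 6, extend the stated use of the DLT-evaluable population, with its Cycle 1 window, to Part B. State that this is an exception to the safety-population default.
3. Show Part A 12 mg/kg and Part B as separate columns in the TEAE, SAE and exposure tables, and replace *study arm* in SAP 6.7.2 with these groups.

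The cost is SAP wording and one extra table column. The study chair already enters DLT and evaluability assessments in the database (Protocol 14.4.2), so no new data or patients are needed.
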